The following events in a participant constitute absolute contraindications to any further dosing of the IP to that participant. If any of these events occur during the study, the participant must not receive additional doses of vaccine but will be encouraged to continue study participation for safety through end-of-study period as defined in [Section 4.4](#).

- Part A only: Diagnosed COVID-19 by detection of SARS-CoV-2 in a Day 1 NP swab sample or COVID-19 diagnosed prior to Day 29. If COVID-19 is suspected on or prior to Day 29, further administration of IP must be withheld until COVID-19 test results are available.
- Anaphylaxis or systemic hypersensitivity reaction following the administration of vaccine.
- Any SAE judged by investigator or Sponsor to be related to study vaccine.
- Any clinically significant medical condition that, in the opinion of the investigator, poses an additional risk to the participant if he/she continues to participate in the study.

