8.1.2. Surveillance for COVID-19 Symptoms

Surveillance for COVID-19 symptoms will be conducted by a combination of safety phone calls and eDiary completion as presented in the SoEs in [Section 11.1](#), in addition to study site visits ([Figure 3](#)). If there is no response to an eDiary prompt for 2 days, the site staff will contact the study participant by phone.

According to the CDC as of 10 Jun 2020 ([CDC 2020c](#)), patients with COVID-19 have reported a wide range of symptoms ranging from mild symptoms to severe illness. Throughout the study, to surveil for COVID-19, the following prespecified symptoms that meet the criteria for suspicion of COVID-19 will be elicited weekly from the participant and the presence of any one of these symptoms lasting at least 48 hours (except for fever and/or respiratory symptoms) will result in the site arranging an Illness Visit to collect an NP swab sample within 72 hours:

- Fever (temperature $\geq 38^{\circ}\text{C}$) or chills (of any duration, including ≤ 48 hours)
- Shortness of breath or difficulty breathing (of any duration, including ≤ 48 hours)
- Cough (of any duration, including ≤ 48 hours)
- Fatigue
- Muscle or body aches
- Headache
- New loss of taste or smell
- Sore throat
- Congestion or runny nose

- Nausea or vomiting
- Diarrhea

It is important to note that some of the symptoms of COVID-19 overlap with solicited systemic ARs that are expected after vaccination with mRNA-1273 (eg, myalgia, headache, fever, and chills). During the first 7 days after vaccination, when these solicited ARs are common, investigators should use their clinical judgement to decide if an NP swab sample should be collected (Part A). The collection of an NP swab sample prior to the Day 1 and Day 29 vaccination can help ensure that cases of COVID-19 are not overlooked. Any study participant reporting respiratory symptoms during the 7-day period after vaccination should be evaluated for COVID-19.

Figure 3: Surveillance for COVID-19 Symptoms and the Corresponding Clinical Data Pathways

Symptoms that meet the criteria for suspicion of COVID-19 infection

- Fever (temperature $\geq 38^{\circ}\text{C}$) or chills
- Cough
- Shortness of breath or difficulty breathing
- Fatigue
- Muscle or body aches
- Headache
- New loss of taste or smell
- Sore throat
- Congestion or runny nose
- Nausea or vomiting
- Diarrhea

Elicited through interaction with the (in person or phone) and/or clinical evaluation by investigator

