 - Respiratory symptom: earliest date of an eligible respiratory symptom is reported
 - Systemic symptoms: earliest date of the 2nd eligible systemic symptom is reported

The time to the first occurrence of COVID-19 will be calculated as:

Time to the 1st occurrence of COVID-19 = Date of documented COVID-19 – Date of randomization +1.

In the primary analysis approach for the primary efficacy endpoint, cases will be counted starting 14 days after the 2nd injection, i.e. date of documented COVID-19 – Date of the 2nd injection \geq 14 (starting 14 days after the 2nd injection).

In the primary analysis approach for the primary efficacy endpoint, the first occurrence of COVID-19 starting 14 days after the 2nd injection will be considered event. In the various sensitivity analyses planned to examine the onset of COVID-19, the censoring rules of cases are outlined in Table 2 below.

In this study, during the blinded phase, there is a scheduled NP swab test at the Day 29 visit prior to the 2nd injection of IP; and blood samples are collected with bAb against SARS-CoV-2 nucleocapsid (NP) tested at months 1, 2, 7, 13 and 25. At IA1 and the Primary Analysis of efficacy, RT-PCR results at scheduled pre-dose 2 (Day 29) and bAb against SARS-CoV-2 nucleocapsid at Day 29 were not considered in the derivation of COVID-19.

At the final blinded efficacy analysis, subjects with early infection, as detected by positive RT-PCR at scheduled pre-dose 2 visit (Day 29), or positive bAb against SARS-CoV-2 NP in blood samples at the scheduled visits, are censored at the time of early infection. If a participant had eligible symptom(s) within 14 days of positive RT-PCR at scheduled pre-dose 2 visit, the participant is considered to be a case for COVID-19.

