6.3.1.3. Sensitivity Analyses with COVID-19 Cases Counted Starting at Various Timepoints

Sensitivity analyses will be performed with COVID-19 cases counted starting at various timepoints as below using the PP Set. The censoring rules for analyses of the primary endpoint are summarized in Table 2.

- immediately after the second injection of IP
- 14 days after the first injection of IP (also as primary analysis approach for the secondary efficacy objective: To evaluate the efficacy of mRNA-1273 to prevent COVID-19 after the first dose of IP.)
- immediately after the first injection of IP
- immediately after randomization

If <10% of the COVID-19 cases received the first injection after the day the subject was randomized, sensitivity analysis with COVID-19 cases counted starting after the first injection of IP may not be performed separately, as it would be very similar to the sensitivity analysis with COVID-19 cases counted starting from randomization.

Table 2: Censoring Rules for COVID-19

Situation	Primary Efficacy Approach (cases ≥ 14 days after Dose 2)	Sensitivity Analyses			
		Cases starting after Dose 2	Cases ≥ 14 days after Dose 1	Cases starting after Dose 1*	Cases starting after randomization
Early case from randomization up to first injection	Censored at date of case	Censored at date of case	Censored at date of case	Censored at date of case	Event
Early case from Dose 1 up to ($<$) 14 days after Dose 1	Censored at date of case	Censored at date of case	Censored at date of case	Event	Event
Early case from ≥ 14 days after Dose 1 up to ($<$) Dose 2	Censored at date of case	Censored at date of case	Event	Event	Event
Early case from Dose 2 up to ($<$) 14 days after Dose 2	Censored at date of case	Event	Event	Event	Event
Case ≥ 14 days after Dose 2	Event	Event	Event	Event	Event
Early discontinuation or death without documentation of COVID-19	Censored at date of discontinuation/death				

Situation	Primary Efficacy Approach (cases \geq14 days after Dose 2)	Sensitivity Analyses			
		Cases starting after Dose 2	Cases \geq14 days after Dose 1	Cases starting after Dose 1*	Cases starting after randomization
Early infection as detected by: positive RT-PCR at scheduled visit (pre-dose 2), or, positive bAb against SARS-CoV-2 NP in blood samples at the scheduled visits	Censored at date of early infection				

* To be performed if there are \geq 10% of total cases with Dose 1 date > randomization date

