6.3.2.1.4. Derivation of asymptomatic SARS-CoV-2 infection

Asymptomatic SARS-CoV-2 infection will be analyzed using the Per-Protocol Set and mITT Set. Asymptomatic infection is identified by absence of symptoms and infections as detected by RT-PCR or seroconversion. Specifically:

- Absent of symptoms (no COVID-19 symptom for either primary efficacy endpoint of COVID-19, or secondary definition of COVID-19),
- AND at least one from below:
 - seroconversion (bAb specific to SARS-CoV-2 nucleocapsid) at scheduled visits (months 1, 2, 7, 13 and 25 if applicable in Part A, Participant Decision Visit and etc. in Part B), when blood samples for immunogenicity are collected, or
 - by RT-PCR at scheduled visits such as pre-dose 2 at Day 29 in Part A, both RT-PCR test and bAb against SARS-CoV-2 nucleocapsid will be considered.

The date of documented asymptomatic infection is the earlier date of seroconversion due to infection, or positive RT-PCR at scheduled visits, with absence of symptoms.

Participants who had a symptomatic infection (COVID-19 or secondary definition of COVID-19) prior to an asymptomatic infection will be censored at the time of symptomatic infection for the analysis of asymptomatic infection. In the primary approach, documented asymptomatic infection is counted starting 14 days after the 2nd IP dose, which requires seroconversion at months 2 (Day 57 visit) or later.

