6.6.2. Solicited Adverse Reactions

An AR is any AE for which there is a reasonable possibility that the test product caused the AE. The term “Solicited Adverse Reactions” refers to selected signs and symptoms occurring after injection administration during a specified post-injection follow-up period (day of injection and 6 subsequent days). The solicited ARs are recorded by the subject in eDiary. The occurrence and intensity of selected signs and symptoms is actively solicited from the subject during a specified post-injection follow-up period (day of injection and 6 subsequent days), using a pre-defined checklist in the eDiary (i.e. solicited ARs).

The following local ARs will be solicited by the eDiary: pain at injection site, erythema (redness) at injection site, swelling/induration (hardness) at injection site, and localized axillary swelling or tenderness ipsilateral to the injection arm.

The following systemic ARs will be solicited by the eDiary: headache, fatigue, myalgia (muscle aches all over the body), arthralgia (aching in several joints), nausea/vomiting, body temperature (potentially fever), and chills.

The solicited ARs will be graded based on the grading scales presented in Table 4 in the protocol, modified from the Toxicity Grading Scale for Healthy Adult and Adolescent Volunteers Enrolled in Preventative Vaccine Clinical Trials ([DHHS 2007](#)). Investigator will assess the Grading for Grade 4 events (with exception of fever).

If a solicited local or systemic AR continues beyond 7 days post injection, the subject will be prompted to capture solicited local or systemic AR in the eDiary until resolution.

All solicited ARs (local and systemic) will be considered causally related to injection.

Analyses of solicited ARs will be provided by treatment group for each injection (first or second) based on the associated subset of Solicited Safety Set, i.e. First (Second) Injection

Solicited Safety Set; and for any injection based on the Solicited Safety Set, unless otherwise specified.

The number and percentage of subjects who reported each individual solicited local AR (has a severity grade of Grade 1 or greater) and solicited systemic AR (has a severity grade of Grade 1 or greater) during the 7-day follow-up period after each injection will be provided by severity grade. The number and percentage of subjects who reported each individual solicited AR will also be summarized by severity grade, days of reporting and injection.

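### The rule that turns a positive pre-Dose 2 swab into a COVID-19 case does not exclude reactions to the Dose 2 given at that visit, which biases several non-primary analyses by an unknown amount

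*SAP*

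**What the plan says.** SAP Part A 6.3.1.1 notes that "there is a scheduled NP swab test at the Day 29 visit prior to the 2nd injection of IP". The first interim analysis and the primary analysis set that result aside. At the final blinded analysis a positive swab at this visit is an early infection and is censored, with one exception: given "eligible symptom(s) within 14 days of positive RT-PCR at scheduled pre-dose 2 visit, the participant is considered to be a case" of COVID-19. A case needs two of six systemic symptoms or one respiratory sign, and its date is the later of the swab and the qualifying symptom.

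Other places that bear on the rule:

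- Protocol 8.1.2 warns that "some of the symptoms of COVID-19 overlap with solicited systemic ARs that are expected after vaccination with mRNA-1273" and names myalgia, headache, fever and chills. SAP Part A 6.6.2 solicits these, plus fatigue and nausea/vomiting, over the "day of injection and 6 subsequent days".
- Protocol 7.2: "If COVID-19 is suspected on or prior to Day 29, further administration of IP must be withheld" until the test result is known.
- SAP Part A Table 2 censors a case between Dose 2 and day 13 in the primary column and counts it as an event in the other four. One of those four is the main analysis of the secondary objective on COVID-19 after the first dose. A separate row, which opens "Early infection as detected by: positive RT-PCR at scheduled visit (pre-dose 2", only censors.
- SAP Part A 6.3.2.1.4 detects asymptomatic infection "by RT-PCR at scheduled visits such as pre-dose 2 at Day 29 in Part A" (among other ways), provided that there is no COVID-19 symptom under either case definition.

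**The concern.** The swab precedes the injection, but a symptom in the following 14 days may be caused by it. A symptom-free carrier is swabbed, dosed, and then recorded as a COVID-19 case if two ordinary vaccine reactions follow. Protocol 8.1.2 deals with the overlap by leaving the decision to swab in the first 7 days to the investigator. That cannot help when the positive swab is already in hand.

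Saline recipients should react less often. Protocol 2.3.3 says that they may be at lower risk of injection-related events, and Protocol 2.2.2 reports that systemic reactions rose after the second injection in the Phase 1 study. The misclassification therefore depends on arm. It adds cases to the symptomatic counts that start before day 14 after Dose 2, and it removes the same people from the asymptomatic analysis.

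The rule also outlives Part A. SAP Part B/C 5.3.1.1 and 5.3.2.1.2 keep it, and 5.3.1.2.1 reuses Part A data from Dose 1, including an interval from Dose 2 to before day 14. Participants first vaccinated in Part A had a pre-Dose 2 swab, whereas Protocol Table 21 schedules none at OL-D29 for the crossover group. Conversions can enter only one side of the relative-effectiveness comparison in 5.3.1.2.1.1.

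**Working it through.** The plan gives no figure for this rule, and the 151-case target does not depend on it. There are four checks.

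**1. Overlap.** Eligible systemic symptoms (SAP Part A Table 1): fever, chills, myalgia, headache, sore throat, smell/taste disorder. Solicited systemic reactions among them: fever, chills, myalgia, headache, so 4 of 6, and any 2 suffice.

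**2. Which counts change.** Take swab day = Dose 2 day = day 0 and case date = max(0, symptom day). A primary event needs a case date of at least 14.

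- Symptom on days 0-6 (solicited window): 0 of 7 onset days give a primary event.
- Symptom on days -14 to 13: 0 of 28.
- Only onset on exactly day 14 does, and that lies outside the solicited window.

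Each conversion on days 0-6 is an event in all four other Table 2 columns.

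**3. Direction.** Let n_p, n_v be symptom-free Day 29 positives (placebo, vaccine), and p_p, p_v the probability of qualifying symptoms unrelated to infection within 14 days.

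- Asymptomatic VE among these positives = 1 - n_v(1-p_v) / [n_p(1-p_p)]. It is inflated whenever p_v > p_p, whatever the carrier counts.
- Symptomatic VE falls whenever n_v·p_v / (n_p·p_p) exceeds the true case ratio.
- Most conversions are in the vaccine arm only if p_v/p_p > n_p/n_v.

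**4. Size, on assumed inputs.** None of these is in the documents: 200 placebo and 12 vaccine true symptomatic cases (ratio 0.06, VE 94.0%), p_p = 0.10, p_v = 0.30 or 0.60, equal person-time. Symptomatic VE = 1 - (12 + n_v·p_v)/(200 + n_p·p_p).

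| n_p / n_v | p_v | Conversions, placebo / vaccine | Vaccine share | Symptomatic VE | Asymptomatic VE, true → observed |
|---|---|---|---|---|---|
| 30 / 10 | 0.30 | 3 / 3 | 50% | 1 - 15/203 = 92.6% | 66.7% → 74.1% |
| 30 / 10 | 0.60 | 3 / 6 | 67% | 1 - 18/203 = 91.1% | 66.7% → 85.2% |
| 40 / 15 | 0.30 | 4 / 4.5 | 53% | 1 - 16.5/204 = 91.9% | 62.5% → 70.8% |
| 40 / 15 | 0.60 | 4 / 9 | 69% | 1 - 21/204 = 89.7% | 62.5% → 83.3% |
| 60 / 25 | 0.30 | 6 / 7.5 | 56% | 1 - 19.5/206 = 90.5% | 58.3% → 67.6% |
| 60 / 25 | 0.60 | 6 / 15 | 71% | 1 - 27/206 = 86.9% | 58.3% → 81.5% |

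The last column covers Day 29 swab positives only. The from-randomization analysis also includes seroconversions, which dilute the effect.

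**Consistency of the text.** SAP Part A Table 1 requires the positive PCR to come from an illness visit prompted by symptoms, which a scheduled swab is not. Table 2's early-infection row censors in every column and omits the exception in 6.3.1.1. For the secondary definition, 6.3.2.1.2 asks for a symptom-prompted PCR and imports Table 2, while 6.3.2.2 says that the Day 29 PCR is considered in the count from Dose 2. SAP Part B/C 5.3.2.1.2 applies the upgrade to the secondary definition outright.

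**The case against.** The strongest reply is that no confirmatory result moves, and that stands. A reader might infer from the rule's place in the primary-endpoint section that primary VE is affected. It is not: these people are censored there under either label. Of the secondary endpoints in the testing sequence (SAP Part A 6.5), COVID-19 regardless of prior infection is counted from 14 days after Dose 2, the infection endpoint counts any positive PCR with or without symptoms, and severe disease needs severity criteria as well. The main asymptomatic analysis uses only seroconversion at Day 57 or later. For symptomatic disease the bias runs against the vaccine.

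Filters also exist. Blinded adjudication is used at the final analysis; SAP Part A limits it to COVID-19 and severe COVID-19, while Protocol 8.4.3 extends it to the primary and secondary endpoints. Solicited reactions are recorded on their own checklist, and most non-respiratory symptoms other than fever or chills prompt an illness visit only after 48 hours. These may remove some conversions, so the table, which converts every reactor, is an upper reading for its inputs. They do not settle the matter. No reactogenicity criterion for adjudication is stated in these documents, the committee does not know the arm, and a symptom-plus-PCR case set is reported beside the adjudicated one.

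In Part B/C most of the exposure is already closed: crossover participants who are positive at the decision visit, and pre-booster positives, are outside the at-risk sets. Only the carried-over Day 29 swab remains.

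**Conclusion.** The point holds for a limited set of analyses: COVID-19 from 14 days after the first dose, the counts from Dose 2, Dose 1 and randomization, the from-randomization asymptomatic sensitivity analysis, and the Part B/C primary-series comparison where it includes time before day 14 after Dose 2. In the Part A analyses, symptomatic VE is biased down and asymptomatic VE up. The direction rests on the documents' qualitative statements about reactogenicity. The size cannot be known from them, and the tabulated values illustrate declared assumptions only.

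A reader might also infer that most converted cases are in the vaccine arm. That is not established. At 30% versus 10% the vaccine share is only 50-56%. If the first dose already prevents a fraction e of Day 29 positives, a vaccine-arm majority needs p_v/p_p above 1/(1-e): 2.0 at e = 50%, 3.3 at 70%, 5.0 at 80%. The bias does not need a majority. Whether the Part A secondary definition is affected is unresolved, because its governing sections disagree.

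**What to change.** For a positive scheduled pre-dose swab, do not count fever, chills, myalgia or headache (and, for the secondary definition, fatigue or nausea/vomiting) toward the case criteria when onset is on the day of injection or in the 6 days after it. All other eligible symptoms still count, including sore throat, smell/taste loss, respiratory signs, congestion and diarrhea, as do any symptoms that start before the dose or after the window. If the criteria are not met, censor the person as an early infection and keep the person eligible for the asymptomatic endpoint.

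Apply this in both arms, and in SAP Part B/C 5.3.1.1 and 5.3.2.1.2 for the carried-over Day 29 swab. Report results under this rule and the current one. SAP Part B/C treats the Part A analyses as completed, so for Part A label it a post hoc sensitivity analysis. Reconcile SAP Part A 6.3.1.1, Tables 1 and 2, 6.3.2.1.2 and 6.3.2.2, and state whether the upgrade applies to the secondary definition.

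The cost is a derivation flag on data already held, plus one more set of tables. The downside is not equal between arms. Some true mild illnesses in the first week become infection only, and more of them are in placebo if placebo has more infections. If 10 placebo and 2 vaccine illnesses moved, an asymptomatic VE of 62.5% (15 versus 40) would become 1 - 17/50 = 66%. Both versions must therefore be shown.

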6.3.1.2. Primary Analysis Approach

The number and percentage of subjects who had an event (i.e. the first occurrence of COVID-19 starting 14 days after the second injection, date of documented COVID-19 – date of the second injection ≥ 14) and subjects who were censored will be summarized.

The non-parametric Kaplan-Meier method will be used to estimate the time to first occurrence of COVID-19 curve in each treatment group.

Vaccine efficacy (VE) is defined as the percent reduction in the hazard of the primary endpoint (mRNA-1273 vs. placebo), i.e. one minus the hazard ratio (HR). The null hypothesis is:

$$H_0^{\text{efficacy}}: \text{vaccine efficacy} \leq 0.3$$

Equivalently, the null hypothesis is:

$$H_0^{\text{efficacy}}: \text{hazard ratio (HR)} \geq 0.7$$

A stratified Cox proportional hazard (PH) model with Efron's method of tie handling and with treatment group as covariate will be used to assess the magnitude of the treatment group difference (i.e. HR) between mRNA-1273 vs. placebo. The same stratification

factors used for randomization ([Section 4.4](#)) will be applied to the stratified Cox model. VE with corresponding alpha-adjusted confidence interval (CI), 95% CI, and one-sided p -value for testing the null hypothesis from the stratified Cox model would be reported at a planned interim analysis up to the analysis at which vaccine efficacy is demonstrated. After vaccine efficacy was demonstrated, VE and 95% CI would be provided for subsequent analysis/updates of efficacy.

In this study, vaccine efficacy was demonstrated based on pre-specified statistical criterion (Section 6.4) at the first interim analysis, at which, one-sided p -value for testing the null hypothesis of $VE \leq 0.3$, 95% CI and alpha-adjusted CI were provided from the stratified Cox model. At the primary analysis where the total number of COVID-19 cases > 151 , total target number of cases, VE, one-sided p -value for testing the null hypothesis of $VE \leq 0.3$ and 95% CI were provided. In subsequent analysis/updates of efficacy, VE and 95% CI will be provided.

For the primary analysis, subjects who have no documented COVID-19 will be censored at the last study assessment date. Subjects who discontinue the study early or die due to causes unrelated to COVID-19 without documented COVID-19 will be censored at the date of early discontinuation or death. Subjects who experience an early COVID-19 up to 14 days after the second injection of IP will be censored at the time of documented COVID-19.

As in PP Set definition, subjects who missed study IP administration, who were seropositive at baseline, or who had major protocol deviations that impact critical or key data, will be excluded from the PP Set.

The number and percentage of subjects who had an event (i.e. the first occurrence of COVID-19 at least 14 days after the second injection) will be reported.

Potential intercurrent events to the estimand are listed in Appendix F Table 9. The primary estimand with rationale for strategies to address intercurrent events is summarized in Appendix F 10.

